4.5.2 Management of Infusion Reactions

4.5.2.1 Guidelines for Elotuzumab Infusion in Subjects with Infusion Reactions

4.5.2.1.1 Grade 1 Infusion Reaction

For Grade 1 elotuzumab infusion-related reactions, by definition, do not require intervention. However, increased monitoring is recommended.

4.5.2.1.2 Grade 2 or 3 Infusion Reaction

Infusion reactions during the elotuzumab infusion: For a Grade 2 or 3 elotuzumab infusion-related reaction, the infusion must be interrupted. The subject should be treated as clinically indicated with one or more of the following medications or interventions: antiemetics, antihistamines, analgesics, corticosteroids, leukotriene inhibitors, oxygen inhalation, epinephrine, bronchodilators, or other supportive measures as indicated.

Once the elotuzumab infusion-related reaction has resolved to Grade ≤ 1 , the infusion can be restarted at 0.5 mL/minute. If symptoms do not recur after 30 minutes, the infusion rate may be increased in a stepwise fashion (0.5 mL/minute every 30 minutes or per investigator's discretion) to the rate at which the infusion reaction occurred. If no recurrence of the infusion reaction, the escalation regimen according to the table above can be resumed.

Subjects who experience an infusion reaction require vital signs to be monitored every 30 minutes for 1 or 2 hours after the end of the elotuzumab infusion (or as clinically indicated per investigator's discretion). If the elotuzumab infusion reaction recurs, the infusion must be stopped and not restarted on that day. Appropriate therapy should be administered to address the subject's signs and symptoms. The infusion can be reattempted at the next protocol defined infusion time point at the investigator's discretion with additional premedication as described in [Table 4.5.1.3-5](#).

Infusion reactions after the completion of elotuzumab infusion: Should a Grade 2 or 3 infusion reaction occur following completion of an elotuzumab infusion, the subject should be treated as above.

Elotuzumab infusions on subsequent weeks after a prior Grade 2 or 3 infusion reaction: Subjects with a prior Grade 2 or 3 infusion reaction during Cycle 1 should have the subsequent infusion started at 0.5 mL/min. The infusion rate may be escalated in a stepwise fashion (0.5 mL/minute every 30 minutes) to the rate at which the infusion reaction occurred. If no Grade ≥ 2 infusion reaction occurs, the escalation regimen may be resumed and the next infusion may be initiated as planned per the regimen.

Contact the Medical Monitor with any questions regarding elotuzumab infusion rate escalation.

4.5.2.1.3 Grade 4 Infusion Reaction

Acute symptoms should be managed as described in [Section 4.5.2.1.2](#). Elotuzumab must be permanently discontinued. Subjects may continue with nivolumab, pomalidomide and dexamethasone per protocol.

4.5.2.1.4 Treatment of Nivolumab-Related Infusion Reactions

Since nivolumab contains only human immunoglobulin protein sequences, it is unlikely to be immunogenic and induce infusion or hypersensitivity reactions. However, if such a reaction were to occur, it might manifest with fever, chills, rigors, headache, rash, pruritus, arthalgias, hypotension, hypertension, bronchospasm, or other allergic-like reactions. All Grade 3 or 4 infusion reactions should be reported within 24 hours to the study medical monitor and reported as an SAE if it meets the criteria. Infusion reactions should be graded according to NCI CTCAE (Version 4.0) guidelines.

Treatment recommendations are provided below and may be modified based on local treatment standards and guidelines, as appropriate:

For **Grade 1** symptoms: (mild reaction; infusion interruption not indicated; intervention not indicated):

- Remain at bedside and monitor subject until recovery from symptoms. The following prophylactic premedications are recommended for future infusions: diphenhydramine 50 mg (or equivalent) and/or acetaminophen/paracetamol 325 to 1000 mg at least 30 minutes before additional nivolumab administrations.

For **Grade 2** symptoms: (moderate reaction required therapy or infusion interruption but responds promptly to symptomatic treatment (eg, antihistamines, non-steroidal anti-inflammatory drugs, narcotics, corticosteroids, bronchodilators, IV fluids); prophylactic medications indicated for ≤ 24 hours):

- Stop the nivolumab infusion, begin an IV infusion of normal saline, and treat the subject with diphenhydramine 50 mg IV (or equivalent) and/or acetaminophen/paracetamol 325 to 1000 mg; remain at bedside and monitor subject until resolution of symptoms. Corticosteroid and/or bronchodilator therapy may also be administered as appropriate. If the infusion is interrupted, then restart the infusion at 50% of the original infusion rate when symptoms resolve; if no further complications ensue after 30 minutes, the rate may be increased to 100% of the original infusion rate. Monitor subject closely. If symptoms recur, then no further nivolumab will be administered at that visit.
- For future infusions, the following prophylactic premedications are recommended: diphenhydramine 50 mg (or equivalent) and/or acetaminophen/paracetamol 325 to 1000 mg should be administered at least 30 minutes before nivolumab infusions. If necessary, corticosteroids (up to 25 mg of SoluCortef or equivalent) may be used.

For **Grade 3 or 4** symptoms: (severe reaction, Grade 3: prolonged [ie, not rapidly responsive to symptomatic medication and/or brief interruption of infusion]; recurrence of symptoms following

initial improvement; hospitalization indicated for other clinical sequelae (eg, renal impairment, pulmonary infiltrates). Grade 4: Life-threatening; pressor or ventilatory support indicated):

- Immediately discontinue infusion of nivolumab. Begin an IV infusion of normal saline and treat the subject as follows: Recommend bronchodilators, epinephrine 0.2 to 1 mg of a 1:1000 solution for subcutaneous administration or 0.1 to 0.25 mg of a 1:10,000 solution injected slowly for IV administration, and/or diphenhydramine 50 mg IV with methylprednisolone 100 mg IV (or equivalent), as needed. Subject should be monitored until the Investigator is comfortable that the symptoms will not recur, nivolumab will be permanently discontinued. Investigators should follow their institutional guidelines for the treatment of anaphylaxis. Remain at bedside and monitor subject until recovery of the symptoms.

In case of late-occurring hypersensitivity symptoms (eg, appearance of a localized or generalized pruritus within 1 week after treatment), symptomatic treatment may be given (eg, oral antihistamine or corticosteroids).

4.5.3 Management Algorithms for Immune Related Adverse Events

Immuno-oncology (I-O) agents are associated with AEs that can differ in severity and duration than AEs caused by other therapeutic classes. Nivolumab is considered an immuno-oncology agent in this protocol. Early recognition and management of AEs associated with immuno-oncology agents may mitigate severe toxicity. Management Algorithms have been developed to assist investigators in assessing and managing the following groups of AEs:

- Gastrointestinal
- Renal
- Pulmonary
- Hepatic
- Endocrinopathy
- Skin
- Neurological

The above algorithms are found in [Appendix 5](#) and in the nivolumab Investigator Brochure.

4.5.4 Dose Delay, Interruption, or Discontinuation, All Subjects

If the dose of one drug in the regimen (ie, pomalidomide, dexamethasone, nivolumab or elotuzumab) is interrupted, or discontinued, the treatment with the other drugs may continue as scheduled. However, if dexamethasone is interrupted or discontinued discuss ongoing elotuzumab administration with the medical monitor (applicable for NE-Pd arm only).

Each cycle is 28 days. While dose delays (within the allowed window determined below for nivolumab and elotuzumab) or interruptions are permitted, the start of each cycle cannot be delayed and is fixed (ie, anchored) relative to Cycle 1 Day 1. Adjustments to the Cycle 1 Day 1 anchored schedule should not be performed. Should the start of a cycle be delayed, it is expected the following cycle begin as anchored to Cycle 1 Day 1. For example, if a subject is unable to start Cycle (X) until 3 days after the anchored start date, all assessments should be recorded on Cycle

(X) Day 3. The following cycle should begin on Day 1 (not Day 3) of Cycle (X+1). Missed doses should be skipped, not delayed, if not given within the allowed window.

Subjects may continue on study therapy even if components of the study therapy must be discontinued.

Please consult the BMS Medical Monitor or any questions regarding dose interruption or study therapy discontinuation.

4.5.4.1 *Elotuzumab*

In Cycles 1 to 2, elotuzumab doses that fall outside of the pre-specified window of -1 to +3 days must be skipped.

Beginning with Cycle 3 and beyond, elotuzumab dosing may be delayed for up to 1 week. If unable to administer within 1 week, then the dose should be skipped and resumption of the elotuzumab continues per the protocol defined schedule.

Subjects experiencing a Grade 4 infusion reaction related to elotuzumab must permanently discontinue elotuzumab.

4.5.4.2 *Dexamethasone*

Dexamethasone interruption should be performed as clinically indicated at the discretion of the investigator.

For subjects receiving elotuzumab, the weekly dexamethasone that coincides with or is temporally closest to the next elotuzumab dosing must be administered as part of the premedication for elotuzumab per the guidance in [Section 4.5.1.3.2](#).

4.5.4.3 *Pomalidomide*

Pomalidomide interruption should be performed as clinically indicated at the discretion of the investigator.

Subjects should be instructed that if a dose of pomalidomide has been missed and it has been less than 12 hours since the subject's regular dosing time, to take pomalidomide as soon as the subject remembers. If it has been more than 12 hours, the dose must be skipped. Subjects should not take 2 doses at the same time.

4.5.4.4 *Nivolumab*

For subjects being dosed in the nivolumab 240 mg Q2W part of the study, they may be dosed no less than 12 days from the previous dose. Nivolumab can be delayed within a 3 day window of Day 1 and Day 15 as long as the 12 day interval between 2 nivolumab 240 mg doses is respected. Doses that fall outside the allowed window should be skipped.

For subjects being dosed in the nivolumab 480 mg Q4W part of the study, for the first dose, it may be dosed no less than 12 days from the previous dose and for subsequent doses it should be dosed no less than 21 days from the previous dose. Nivolumab can be delayed within a 7 day window of Day 1 as long as the 12 day and 21 day intervals for the first 480 mg dose and subsequent 480 mg

doses, respectively, between 2 nivolumab doses is respected. Doses that fall outside the allowed window should be skipped.

A pattern of immune-related AEs (IMAEs) has been defined in subjects treated with nivolumab, for which management algorithms have been developed. [Appendix 5](#) includes these comprehensive algorithms for supportive care, by system organ and by severity (See [Section 4.5.3](#)).

4.5.4.4.1 Dose Delay/Interruption Criteria for Nivolumab

Nivolumab administration should be delayed for the following:

- Grade 2 non-skin, drug-related AE, with the exception of fatigue
- Grade 2 drug-related creatinine, AST, ALT and/or Total Bilirubin abnormalities
- Grade 3 skin, drug-related AE
- Grade 3 drug-related laboratory abnormality, with the following exceptions:
 - Grade 3 lymphopenia or asymptomatic amylase or lipase does not require dose delay
 - Grade ≥ 3 AST, ALT, Total Bilirubin will require dose discontinuation (see [Section 4.5.4.4.3](#))
- Any adverse event, laboratory abnormality, or intercurrent illness which, in the judgment of the investigator, warrants delaying the dose of study medication.

Participants who require delay of nivolumab should be re-evaluated weekly or more frequently if clinically indicated and resume nivolumab dosing when re-treatment criteria are met.

Additional criteria for nivolumab dose delay/interruption are included in the nivolumab IMAE management algorithm in Appendix 5.

4.5.4.4.2 Criteria to Resume Treatment with Nivolumab

Subjects may resume treatment with nivolumab when the drug-related AE(s) resolve(s) to Grade ≤ 1 or baseline, with the following exceptions:

- Subjects may resume treatment in the presence of Grade 2 fatigue.
- Subjects who have not experienced a Grade 3 drug-related skin AE may resume treatment in the presence of Grade 2 skin toxicity.
- For participants with Grade 2 AST, ALT and/or Total Bilirubin abnormalities, dosing may resume when laboratory values return to baseline and management with corticosteroids, if needed, is complete.
- Drug-related pulmonary toxicity, diarrhea or colitis must have resolved to baseline before treatment is resumed. Participants with persistent Grade 1 pneumonitis after completion of a steroid taper over at least 1 month may be eligible for retreatment if discussed with and approved by BMS Medical Monitor (or designee).

Participants with drug-related endocrinopathies adequately controlled with only physiologic hormone replacement may resume treatment after consultation with the BMS Medical Monitor (or

designee). Adrenal insufficiency requires discontinuation regardless of control with hormone replacement.

Dose delay/interruption of nivolumab which results in treatment interruption of > 8 weeks require treatment discontinuation, with exceptions as noted in Section 4.5.4.4.3. There will be no dose reductions for nivolumab.

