4.5.4.4.3 Nivolumab Dose Discontinuation

Nivolumab treatment should be permanently discontinued for the following:

- Any Grade 2 drug-related uveitis, eye pain or blurred vision that does not respond to topical therapy and does not improve to Grade 1 severity within the re-treatment period OR requires systemic treatment
- Any Grade 3 non-skin, drug-related AE lasting > 7 days or recurs, with the following exceptions for laboratory abnormalities, drug-related uveitis, pneumonitis, bronchospasm, neurologic toxicity, hypersensitivity reactions, infusion reactions, and endocrinopathies:
 - Grade 3 drug-related uveitis, pneumonitis, bronchospasm, neurologic toxicity, myocarditis, hypersensitivity reaction, or infusion reaction of any duration requires discontinuation
 - Grade 3 drug-related endocrinopathies adequately controlled with only physiologic hormone replacement do not require discontinuation. Adrenal insufficiency requires discontinuation regardless of control with hormone replacement.
 - Grade 3 drug-related laboratory abnormalities do not require treatment discontinuation except:
 - ◆ Grade 3 drug-related thrombocytopenia > 7 days or associated with bleeding requires discontinuation
 - ◆ Grade \geq 3 drug-related AST, ALT or Total Bilirubin requires discontinuation*
 - ◆ Concurrent AST or ALT $>$ 3 x ULN and total bilirubin $>$ 2x ULN

* In most cases of Grade 3 AST or ALT elevation, study treatment will be permanently discontinued. If the investigator determines a possible favorable benefit/risk ratio that warrants continuation of study treatment, a discussion between the investigator and the BMS Medical Monitor/designee must occur.

- Any Grade 4 drug-related adverse event or laboratory abnormality (including but not limited to creatinine, AST, ALT, or Total Bilirubin), except for the following events which do not require discontinuation:
 - Grade 4 neutropenia \leq 7 days
 - Grade 4 lymphopenia or leukopenia or asymptomatic amylase or lipase
 - Isolated Grade 4 electrolyte imbalances/abnormalities that are not associated with clinical sequelae and are corrected with supplementation/appropriate management within 72 hours of their onset

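### For a combined Grade 2 rise with AST or ALT above 3x ULN and bilirubin above 2x ULN, the nivolumab resume and discontinuation rules point different ways, and no visible text says which governs

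*Combined protocol and SAP*

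**What the plan says.** Three consecutive subsections of the protocol govern nivolumab after a liver abnormality.

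- **Section 4.5.4.4.1 (delay)** lists "Grade 2 drug-related creatinine, AST, ALT and/or Total Bilirubin abnormalities" among the reasons to delay a dose. It refers AST, ALT or bilirubin values to the discontinuation section only from Grade 3 upward.
- **Section 4.5.4.4.2 (resume)** states: "For participants with Grade 2 AST, ALT and/or Total Bilirubin abnormalities, dosing may resume when laboratory values return to baseline", with the further condition that "management with corticosteroids, if needed, is complete". Its only pointer to Section 4.5.4.4.3 concerns interruptions longer than 8 weeks.
- **Section 4.5.4.4.3 (discontinue)** opens with "Nivolumab treatment should be permanently discontinued for the following". One of its bullets reads "Grade 3 drug-related laboratory abnormalities do not require treatment discontinuation except", followed by three exceptions. The first is thrombocytopenia. The second covers Grade 3 or higher liver values ("drug-related AST, ALT or Total Bilirubin requires discontinuation") and carries an asterisk. The third is "Concurrent AST or ALT $>$ 3 x ULN and total bilirubin $>$ 2x ULN", with no asterisk and no grade. The asterisk footnote says that Grade 3 AST or ALT elevation usually ends treatment, but lets the investigator raise continuation with the Medical Monitor on benefit/risk grounds.

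Section 6.6 uses the same 3x and 2x limits to define potential drug-induced liver injury. It adds two conditions (no initial cholestasis, no other apparent cause) and requires SAE reporting. It gives no dosing rule for nivolumab.

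**The concern.** The delay and resume rules say and/or, so they cover AST/ALT and bilirubin raised together, and neither makes an exception for the combined pattern. The discontinuation list names that pattern by numeric limits. One investigator can read the combined item as confined to Grade 3, because of the bullet above it, and resume nivolumab once values are at baseline. Another can take the 3x and 2x limits as written and stop permanently. Both would be following the text.

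Two things are at stake. The first is the safety of subjects still receiving nivolumab, for whom the protocol treats this pattern as a possible serious liver signal. The second is the consistency of the discontinuation and exposure data, since the same laboratory picture could be handled and recorded differently from site to site.

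**Working it through.** The plan states no figure here to reproduce. The check compares the sets of values that each rule covers.

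**1. Notation.** Let a be AST or ALT and b total bilirubin, each as a multiple of ULN. Let A and B be the upper ends of Grade 2 for a and b. The protocol grades by CTCAE v4.0 but prints no limits, so A and B are assumptions.

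**2. The rules for drug-related values.**

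| Section | Applies when | Consequence |
|---|---|---|
| 4.5.4.4.1 | a and/or b at Grade 2 | delay |
| 4.5.4.4.2 | a and/or b at Grade 2, back to baseline, any corticosteroid management finished | may resume |
| 4.5.4.4.3, Grade 3 or higher item (asterisk) | a > A or b > B | permanent discontinuation; continuation may be discussed for Grade 3 AST/ALT |
| 4.5.4.4.3, combined item (no asterisk) | a > 3 and b > 2 | permanent discontinuation |

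**3. Overlap of the resume rule and the combined item.** Both apply when 3 < a ≤ A and 2 < b ≤ B, provided those values lie within Grade 2.

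- If Grade 2 is >3 to 5x for AST/ALT and >1.5 to 3x for bilirubin (A = 5, B = 3), the overlap is >3 to 5x with >2 to 3x ULN.
- For other limits the overlap runs from 3 to A by 2 to B. It is empty only if A ≤ 3 or B ≤ 2.

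**4. Outside the overlap there is no conflict.** An isolated Grade 2 rise, or a combined Grade 2 rise with b ≤ 2, meets only the delay and resume rules. Any value at Grade 3 or above is outside the resume rule for Grade 2.

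**5. What the combined item does if confined to Grade 3.** It still has a function. For Grade 3 AST/ALT with b > 2, the asterisked item leaves continuation open to discussion, while the combined item has no such route. But if Grade 3 AST/ALT starts above 3x ULN, a > 3 is then met automatically and only the bilirubin limit does any work. If bilirubin alone is at Grade 3, the asterisked item already applies, and its footnote speaks only of AST or ALT. On that reading the 3x limit changes an outcome only when neither value is at Grade 3, which is where the delay and resume rules apply. This suggests that the item was meant to reach below Grade 3. It does not prove it.

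**6. Search for a rule of precedence.** None is visible in the three subsections. Section 4.5.4.4.2 does repeat a discontinuation override for adrenal insufficiency, but has none for the liver combination.

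**The case against.** The strongest reply has four parts.

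- **The combined item may belong only to Grade 3.** Because it lacks the asterisk, it has a use inside its parent bullet and need not touch the Grade 2 resume rule. This stands as a possible reading, and it defeats any claim that the item is redundant. It does not settle the matter: the item states no grade, and on this reading its 3x limit has no effect.
- **Permanent discontinuation naturally outranks permission to resume.** The resume rule is permissive and the discontinuation list is directive. Section 4.5.4.4.3 also stops nivolumab for some Grade 2 eye events with no matching exception in the delay or resume lists. This is a fair reading and may be the intended one. But the precedence is not written down, and Section 4.5.4.4.1 refers only Grade 3 or higher liver values to the discontinuation section.
- **Appendix 5 may resolve it.** Sections 4.5.4.4.1 and 4.5.4.4.3 both point there for additional criteria, and the hepatic algorithm is a figure not shown in the text available. It might state one consequence. The body sections would still need to agree with it.
- **There are backstops.** Potential drug-induced liver injury is reportable as an SAE within 24 hours, and the investigator may stop nivolumab for any laboratory abnormality judged a substantial clinical risk. These reduce the danger but do not say what to do with nivolumab for this pattern.

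**Conclusion.** The inconsistency holds in a narrow form. For a drug-related rise with AST or ALT above 3x ULN and bilirubin above 2x ULN, both at Grade 2, the protocol calls for delay with permission to resume in two subsections and lists the same values for permanent discontinuation in a third. It is unclear whether that third rule applies below Grade 3. The size of the overlap, >3 to 5x with >2 to 3x ULN, rests on assumed grade limits.

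A reader might infer more than the documents support:

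- **That the combined item does nothing and could be deleted.** The missing asterisk gives it a function.
- **That the whole protocol gives opposite orders.** The hepatic algorithm is unseen, so only the visible text can be judged.
- **That 75 + 24 = 99 subjects plus crossovers are affected.** The 75 and 24 are subjects randomised to the N-Pd and NE-Pd arms. Enrollment is closed, deaths were already 29% and 50% in those arms, and neither the number still on nivolumab nor the frequency of the pattern is given.
- **That subjects with Gilbert syndrome, admitted with bilirubin up to 3.0x ULN, already meet half the criterion.** The parent bullet concerns drug-related abnormalities, which a pre-existing raised bilirubin is not.
- **That every such case is drug-induced liver injury.** Section 6.6 requires two further conditions.

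**What to change.** Reconcile Sections 4.5.4.4.1, 4.5.4.4.2 and 4.5.4.4.3 so that a combined AST/ALT and bilirubin rise with both values at Grade 2 has one stated consequence. Check the result against the Appendix 5 hepatic algorithm and the potential drug-induced liver injury definition in Section 6.6. State whether the combined criterion applies below Grade 3, and whether the asterisk footnote applies to it. The choice of consequence is the sponsor's clinical decision, and the criterion should not be removed on the ground of redundancy.

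The cost is protocol wording only. No new tests are needed, since the Section 5.1 schedules already include serum chemistry on Day 1 of cycles. The change still matters after closure of enrollment, because subjects on N-Pd and NE-Pd may continue treatment.
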